8.8. Suicidal Risk Monitoring

Baseline and treatment-emergent suicidal ideation and behavior will be assessed during the study using the C-SSRS which will be administered at each in-clinic visit. This scale consists of a baseline evaluation that assesses the lifetime experience of the subject with suicidal ideation and behavior, and a post-baseline evaluation that focuses on suicidality since the last study visit. The C-SSRS includes “yes” or “no” responses for assessment of suicidal ideation and behavior as well as numeric ratings for severity of ideation, if present (from 1 to 5, with 5 being the most severe).

Tables will include results from the Suicidal Ideation and Suicidal Behavior sections of the C-SSRS. Frequencies and percent of subjects with a response of “Yes” at any point on the Suicidal Ideation and Suicidal Behavior items will be summarized by overall subjects. Screening (lifetime and past 6 months), baseline (“pre-treatment”), and post-baseline (“post-treatment”) results will be presented.

Suicidality data collected on the C-SSRS will be listed for all subjects.

8.9. Testicular Ultrasound

A testicular ultrasound will be performed before first dose and at Week 12 in selected male subjects. If there are testicular adrenal rest tumors (TART) lesions present at baseline, a change in tumor size (i.e., sum of the size of all tumors) after treatment will be summarized by cohort and overall male subjects with TARTs at baseline in the FAS. Additionally, change in the number of TARTs from baseline to postbaseline will be summarized. In this context, baseline is the value before first dose.

If historical TART data exist, they will be presented in a listing along with the ultrasound

9. EFFICACY

9.1. General Considerations

For all efficacy data analyses, the safety analysis set will be used unless otherwise specified.

For all endpoints, nominal p-values will be provided.

9.2. Statement of the Null and Alternate Hypotheses for the Hormone Endpoints

The estimate of interest, change from baseline [17-OHP; ACTH; A4; Testosterone], is used to evaluate the effectiveness of SPR001 therapy in CAH subjects.

The following hypothesis testing schema will be employed to assess each endpoint:

The null hypothesis for the comparison will be that there is no difference between the baseline and the Week 12 mean response for [17-OHP; ACTH; A4; Testosterone].

The alternative hypothesis will be that there is a difference.

9.3. Subgroup Analyses

Subgroup analyses will characterize the consistency of the treatment effect across select subject subgroups. Subgroups analyses using the pre-specified subgroups in Section [6.4.5](#) will be repeated for select analyses as specified in subsequent SAP sections.

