4.3. Sample Size Considerations

The sample size of up to approximately 24 subjects in this study is based on an estimate of the number of subjects who may enroll either after completing Study SPR001-201 or as SPR001-naïve subjects. There is no statistical basis for the sample size,

The final sample size for the study is n=11.

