6.4.5. Examination of Subgroups

The following subgroups are pre-defined:

1. Sex: [a] male, [b] female
2. Baseline hormone control: [a] severe/moderate control issues, [b] mild control issues
3. Baseline Glucocorticoid category: [a] Non-Dexamethasone [b] Dexamethasone

Selected analysis will be conducted using the subgroup analysis sets.

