9.5. Analysis of Secondary Efficacy Endpoints

Analysis of hormone data will be conducted only on subgroups.

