9.5.2. Efficacy Analysis of Hormones by Subgroups

To characterize the consistency of the treatment effect for the primary endpoint, each hormone will be summarized using a combination of subgroups

A summary of [17-OHP; ACH; A4; Testosterone] by Visit: [subgroup] will be provided. The following subgroups will be summarized in separate summaries:

- Non-Dexamethasone subjects
- Non-Dexamethasone subjects with severe/moderate control issues
- Non-Dexamethasone subjects with mild control issues

Figures

A serial figure with week as the x-axis and % change as the y-axis will be provided.

Separate serial figures will be provided for each hormone.

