11. APPENDICES

11.1. Reporting Formats

C: Continuous endpoints will be presented with an 8-point summary using the following reporting structure, unless otherwise noted,

N	x
Mean (SD)	x.xx (x.xxxx)
Median	x
Q1, Q3	xx.x, xx.x
Minimum, Maximum	xx.x, xx.x

GM: Continuous endpoints reported in log scale with a Geometric mean

n	x
Geometric Mean (CV)	x.xx (x.xxxx)
95 CI for Geometric mean	x.xx, x.xx
95 CI for Geometric mean Ratio (GMR)	x.xx
95 CI for GMR	x.xx, x.xx

Percentage Change from Baseline	0.xx
95% CI for Percentage Change	x.xx, x.xx

F: Frequency endpoints will be presented by a 3-point summary using the following reporting structure, unless otherwise noted,

Count (%)	x (xx.x)
-----------	----------

MF Categorical variables (multiple frequency) will be presented by a 3-point summary using the following reporting structure, unless otherwise noted, where the sum of the category n's is the total n

n	x
Category 1 count (%)	x (x.x)
Category 2 count (%)	x (x.x)

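### The SAP sets out to characterize consistency of the hormone effect across subgroups but estimates no between-subgroup quantity, so at n=11 chance differences between separate summaries could be read as differences in effect.

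*SAP*

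**What the plan says.** SAP 9.3 gives the purpose: "Subgroup analyses will characterize the consistency of the treatment effect across select subject subgroups". SAP 9.5.2 restates it for the hormones: "To characterize the consistency of the treatment effect for the primary endpoint, each hormone will be summarized using a combination of subgroups". (The hormones are secondary endpoints; that slip does not affect this point.)

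The form of the analysis is in the same section: "The following subgroups will be summarized in separate summaries". The GM format in SAP 11.1 holds only one-group quantities: geometric mean, ratio to baseline, a row labelled "Percentage Change from Baseline", and their 95% CIs. The hypothesis in SAP 9.2 compares baseline with Week 12, and SAP 9.1 adds "For all endpoints, nominal p-values will be provided".

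SAP 9.5 narrows the hormone work further: "Analysis of hormone data will be conducted only on subgroups". In the index in SAP 11.3, 17-OHP, ACTH and A4 have tables for dexamethasone, non-dexamethasone severe/moderate and non-dexamethasone mild subjects. Testosterone has tables overall, for males and for females.

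One of the three factors in SAP 6.4.5 is "Baseline hormone control: [a] severe/moderate control issues, [b] mild control issues". SAP 6.6.3 defines these classes from baseline ACTH and A4. SAP 4.3 states "The final sample size for the study is n=11".

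**The concern.** Consistency is a question about the difference between groups. The plan reports each group against its own baseline and stops there. A reader who wants the answer promised in 9.3 can only lay one subgroup's interval or p-value beside another's.

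That comparison misleads when groups are small or unequal. Each group may or may not exclude no change largely because of its size and noise, so one clear result beside one unclear result is common even when the true effects are identical. For 17-OHP, ACTH and A4 the index has no all-subject change table to serve as an anchor.

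At stake is a conclusion that the drug works in one glucocorticoid group or control class and not in another. SAP 5.1.3 says data cuts may inform later development, so such a reading could shape who is selected for future studies.

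**Working it through.** **Plan's own figure.** There is none to reproduce. Neither document states power, precision, subgroup sizes, an SD or an effect size for the hormone subgroups, and SAP 4.3 says the sample size has no statistical basis. The only power statement (protocol 9.1, TART shrinkage in about 8 males) concerns another endpoint.

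**What is planned.** SAP 9.5.2, the GM format in 11.1 and the index in 11.3 contain no difference, ratio of geometric mean ratios (GMRs) or interaction. Protocol 9.3.9 plans descriptive summaries by sex and prior exposure, also without a contrast.

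**Inputs.** From the documents: n=11, two-sided alternative (SAP 9.2), 95% intervals (SAP 11.1). Assumed: subgroup sizes; a common true effect d, in SDs of within-subject log change; normal log change; two-sided 0.05; t-based intervals.

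**Step 1. Chance that one subgroup excludes no change.** This is the power of the one-sample t test, from the noncentral t with n−1 df and noncentrality d×√n:

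| n | d=1 | d=1.5 | d=2 |
|---|---|---|---|
| 3 | 0.179 | 0.316 | 0.471 |
| 4 | 0.289 | 0.533 | 0.755 |
| 5 | 0.401 | 0.711 | 0.909 |
| 6 | 0.507 | 0.833 | 0.971 |
| 8 | 0.681 | 0.951 | 0.998 |

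**Step 2. Chance that exactly one of two does so when the true effects are equal.** P1(1−P2) + P2(1−P1). For 5 versus 3 at d=1: 0.401×0.821 + 0.179×0.599 = 0.44.

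| sizes | d=1 | d=1.5 | d=2 |
|---|---|---|---|
| 5 vs 3 | 44% | 58% | 52% |
| 4 vs 4 | 41% | 50% | 37% |
| 8 vs 3 | 62% | 67% | 53% |
| 5 vs 6 | 50% | 36% | 12% |

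The first three rows span 37% to 67%. At d=3 the rate is 6% for 4 versus 4 and 0.2% for 5 versus 6, but still 26% for 5 versus 3. Simulation agrees with these figures. In the same simulations a direct two-sample t test on log change was significant in 4.9% to 5.1% of trials.

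**Step 3. Precision of a direct contrast.** The 95% CI for the ratio of GMRs extends by a factor exp(t × SD × √(1/n1+1/n2)) either way.
- 5 versus 3: t(6 df) = 2.447 and √(1/5+1/3) = 0.730. The factor is exp(2.447×0.730×0.5) = 2.4 at a log SD of 0.5, and 4.2 at 0.8.
- 8 versus 3: the half-width is 1.53 SD. The factor is exp(1.53×0.5) = 2.1 at 0.5, and 3.4 at 0.8.
- Power for a true difference of 1 SD is 21% (5 versus 3) to 26% (8 versus 3).

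**Step 4. The control classes are different.** They are set on the same baseline ACTH and A4 from which change is measured. Take equal true effects of −0.5, log SD 1 at both visits, and a split at the median. With a baseline-to-Week 12 correlation of 0.7, mean change is −0.74 in the high half and −0.26 in the low half. The two-sample test then signals a difference in about 12% of trials (5 versus 3 and 4 versus 4). At a correlation of 0.5 it does so in 17% to 18%. The 5% rate from Step 2 does not carry over to this factor.

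**The case against.** The strongest reply is that the SAP promises little. Its verb is characterize, not test. SAP 9.4 calls the study hypothesis generating, no rule for declaring inconsistency is set, and no text plans to compare p-values across subgroups. The GM format has no p-value row, and its intervals already display imprecision. This stands as a limit on severity. It does not turn one-group tables into an assessment of consistency.

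A reader might go further in several ways that the documents do not support:

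- **That subgroups of 3 to 8, or a 37% to 67% rate, are facts about this trial.** Only n=11 is documented. Sizes, SDs and effects are assumptions, and the rate depends heavily on them.
- **That the rate applies whichever test is used.** Protocol 9.3.6 also allows the Wilcoxon signed rank test, whose smallest two-sided p is 2/2^n: 0.25, 0.125 and 0.0625 for n = 3, 4 and 5. On those p-values 5 versus 3 and 4 versus 4 could never disagree at 0.05, while in 8 versus 3 the smaller group could never be significant. The percentages above are for t-based results.
- **That a direct contrast would settle consistency.** The scatter comes from small groups. A contrast makes the uncertainty visible, but with 21% to 26% power for a 1-SD difference it cannot establish consistency.
- **That a contrast is clean for every factor.** Step 4 shows it is not for severe/moderate versus mild.
- **That the within-subgroup p-values should go.** Given SAP 9.5 and the index, they are the only planned tests of the 9.2 hypotheses for 17-OHP, ACTH and A4.

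**Conclusion.** The point stands in limited form. The stated aim and the planned output do not match: consistency is named in two sections and no between-subgroup quantity is estimated anywhere. Under the assumptions in the working, equal true effects would give a split verdict in about 37% to 67% of trials for 5 versus 3, 4 versus 4 and 8 versus 3, and as few as 12% for 5 versus 6 at 2 SD. The mismatch does not depend on these assumptions; the size of the risk does.

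This is an interpretive risk in a small exploratory study, not an error in the within-subgroup estimates. It is worth correcting because it needs no new data and because subgroup impressions may guide later work.

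**What to change.** In SAP 9.3 and 9.5.2:

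1. Add one small table. For each hormone at Week 12, give the ratio of GMRs with its 95% CI (two-sample comparison of log change) for dexamethasone versus non-dexamethasone. For testosterone, also give males versus females.
2. State that differing within-subgroup p-values or CIs are not evidence of inconsistency.
3. Keep the within-subgroup p-values.
4. For severe/moderate versus mild, make no consistency claim and label the tables descriptive. If a contrast is shown, state beside it that regression to the mean can produce a difference under equal true effects.

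Two details need care. SAP 9.5.2 lists an all-non-dexamethasone summary but no dexamethasone one, and the index does the reverse for 17-OHP, ACTH and A4, so the two should be aligned. The non-dexamethasone side should include every such subject: the class definitions in 6.6.3 leave unclassified anyone with only one of ACTH and A4 above twice ULN, so the two class tables need not add up to the whole group.

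The cost is one added table, a few sentences and no new data. The downside is wide intervals, a factor of about 2.4 to 4.2 either way for 5 versus 3 at an assumed log SD of 0.5 to 0.8. They will usually show that consistency cannot be judged at this sample size.

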9.4. Multiple Comparisons and Multiplicity

No control for multiplicity is planned given the hypothesis generating nature of this study.

9.5. Analysis of Secondary Efficacy Endpoints

Analysis of hormone data will be conducted only on subgroups.

9.5.1. Efficacy Analysis of Hormones

Hormones [17-OHP; ACTH; A4; Testosterone] will be summarized using geometric means and geometric means ratios to assess change and percentage change.

A summary of [17-OHP; ACTH; A4; Testosterone] by Visit will include the observed parameter (using GM reporting format).

Figures

A serial figure with week as the x-axis and % change as the y-axis will be provided.

Separate serial figures will be provided for each hormone.

9.5.2. Efficacy Analysis of Hormones by Subgroups

To characterize the consistency of the treatment effect for the primary endpoint, each hormone will be summarized using a combination of subgroups

A summary of [17-OHP; ACH; A4; Testosterone] by Visit: [subgroup] will be provided. The following subgroups will be summarized in separate summaries:

- Non-Dexamethasone subjects
- Non-Dexamethasone subjects with severe/moderate control issues
- Non-Dexamethasone subjects with mild control issues

Figures

A serial figure with week as the x-axis and % change as the y-axis will be provided.

Separate serial figures will be provided for each hormone.

9.6. Analysis of the Exploratory Efficacy Endpoints

9.6.1. Patient Reported Outcomes

Data for the SF-36 (individual domain scores and summary scores), and total score for the CAH signs and symptoms interview will be summarized using descriptive statistics and presented by visit.

Data for PGIC will be summarized using counts and percentages for each SPR001 dose level.

9.6.2. Changes in Lipid Profile

The following parameters will be repeated from the standard lab output and as a standalone summary, changes in lipid profile summary by visit:

- Cholesterol
- HDL Cholesterol
- LDL Cholesterol
- Triglycerides

9.6.3. Changes in Insulin profile

The following parameters will be repeated from the standard lab output and as a standalone summary, changes in insulin profile summary by visit:

- Hemoglobin A1C
- Glucose

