 Subjects should be on a stable regimen of glucocorticoid replacement for a minimum of 12 weeks before baseline and throughout the treatment period. On the mornings of all study visits, including screening, subjects should hold off on taking any morning glucocorticoid medication until after laboratory assessments have been completed. On all other days during the study, subjects may take any morning dose of glucocorticoid medication at their usual time.

	Screening Period	Treatment Period								Follow-up/ET
		2 Baseline	3	4	5	6	7	8	9	
VISIT NUMBER	1 Screening									
STUDY WEEK		0	2	4	6	8	10	12	16	
STUDY DAY	12 weeks before Day 1	1	15	29	43	57	71	85		Last dose +30 days
Site Visits	X	X		X		X		X	X	
Home Visits			X		X		X			
Clinical laboratory 	X	X	X	X	X	X	X	X	X	
HbA1c and fasting insulin 		X		X		X		X		
Key hormones 	X	X	X	X	X	X	X	X	X	
Exploratory adrenal hormones 		X		X		X		X		
PK 	X	X		X		X		X	X	
Hepatitis B & C and HIV screening 	X									
eGFR for screening 	X									
Pregnancy test for WOCP 	X	X		X		X		X	X	
Vital signs  and body weight	X	X	X	X	X	X	X	X	X	
Physical examination 	X	X		X		X		X	X	

 Samples for these lab assessments will be obtained at the beginning of each study visit (8am), after overnight fast (nothing to eat since the previous midnight), and before the subject has taken any morning dose of glucocorticoid medication. If a morning dose of study drug is added, samples for these lab assessments will be obtained before the morning dose of study drug for that day (where applicable).

 Clinical laboratory assessments include hematology, clinical chemistry, fasting glucose, lipid panel, thyroid panel, urinalysis, LH, FSH, inhibin B, SHBG, renin, aldosterone, and, for females only, estradiol, prolactin, and progesterone.

 ACTH, 17-OHP, androstenedione, testosterone, and background glucocorticoid levels (cortisol/prednisolone/dexamethasone, depending on what the subject is taking) will be measured from blood samples. 17-OHP will also be measured from a saliva sample.

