### 3 OBJECTIVES AND ENDPOINTS

Objectives	Endpoints
Primary	
• To evaluate the safety of SPR001 in subjects with CAH	

• AEs, SAEs, AEs leading to discontinuation/withdrawal, DLTs, and AESIs

• Physical examination findings

• Vital signs

• Changes in ECG

• Changes in clinical laboratory values

• Changes in the C-SSRS and the HADS

Secondary	
• To evaluate the efficacy of SPR001 in subjects with CAH in terms of changes in hormones	

• Changes in ACTH, 17-OHP, androstenedione, and testosterone

Exploratory	
• To evaluate the effect of SPR001 on QoL, metabolic parameters, exploratory adrenal hormones, and sex-specific outcomes in subjects with CAH	

• Changes in QoL as measured using the SF-36, PGIC, bother score, and CAH signs and symptoms interview

• Changes in fasting glucose, HbA1c, fasting insulin, and lipid profile

• Changes in BW and BMI

• Changes in exploratory adrenal hormones

• Changes in TARTs and on semen analysis in male subjects

• Changes in acne, hirsutism, and menstrual cyclicity in female subjects

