#### **8.5.1.3 Bother Score**

The bother score is a 1-question survey that asks subjects to evaluate the overall bothersomeness of their CAH symptoms. Subjects select a response on a 7-point scale.

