### **9.3.6 Efficacy Analyses**

Efficacy analyses will be performed on both the Safety and Per Protocol Populations.

Changes over time in hormones (ACTH, 17-OHP, androstenedione, testosterone, and exploratory adrenal hormones) will be summarized using descriptive statistics and presented in tables and/or graphs. Parametric (paired t test) or nonparametric (Wilcoxon signed rank) tests will be used to test the change from baseline depending on the data distribution.

Data for the SF-36 (including individual domain scores and summary scores) will be summarized using descriptive statistics. Data for the PGIC, the bother score, and the CAH signs and symptoms interview will be summarized using counts and percentages. Shifts in status from baseline to each post-baseline visit will be presented.

Changes over time in metabolic parameters (including fasting glucose, HbA1c, fasting insulin, lipid profile, BW, and BMI) will be summarized using descriptive statistics.

Changes over time in measures of TARTs and on semen analysis in male subjects and in measures of acne, hirsutism, and menstrual cyclicity in female subjects will be summarized using descriptive statistics.

Additional analyses may be performed if warranted upon review of the data.

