3.1.3. Exploratory Objectives

The exploratory objectives are:

- To evaluate the effect of SPR001 on quality of life (QoL), metabolic parameters, exploratory adrenal hormones, and sex-specific outcomes in subjects with CAH.

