9.6.5. Bother Score

Subjects scored their most bothersome symptom (symptom was not collected) on a scale of 1 (not bothersome) to 7 (most bothersome; bothersome all the time). A summary of the magnitude of bothersome symptoms will summarize the score and change from baseline in the score using the C reporting format.

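### The SAP departs from the protocol on four exploratory items (fasting insulin, exploratory adrenal hormones, the CAH interview and the bother score) and section 5.1.1 declares none of them

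*SAP*

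**What the plan says.** **Fasting insulin.** Protocol section 3 lists "Changes in fasting glucose, HbA1c, fasting insulin, and lipid profile" as exploratory endpoints. The Schedule of Activities (protocol 1.3) has a row for "HbA1c and fasting insulin" at baseline and Weeks 4, 8 and 12, and protocol 9.3.6 commits to a descriptive summary of change. SAP 3.2.3 lists glucose, HbA1c, lipids, weight and BMI without insulin. The SAP schedule row (4.5) reads HbA1c alone. SAP 9.6.3 promises "changes in insulin profile summary by visit" and then names two parameters, HbA1c and glucose; Table 14.2.9 keeps the insulin title.

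**Exploratory adrenal hormones.** SAP 3.1.3 still sets out to evaluate "metabolic parameters, exploratory adrenal hormones, and sex-specific outcomes in subjects with CAH", and the SAP schedule still draws the sample. SAP 3.2.3 does not list these hormones, SAP 9.5.1 covers 17-OHP, ACTH, A4 and testosterone only, and no table or figure title in SAP 11.3 names them. Protocol 9.3.6 both summarises them and tests their change from baseline.

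**CAH interview.** Protocol 9.3.6 says that data for the PGIC, "the bother score, and the CAH signs and symptoms interview will be summarized using counts and percentages", with shifts from baseline at each later visit. SAP 9.6.1 says instead that the "total score for the CAH signs and symptoms interview will be summarized using descriptive statistics".

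**Bother score.** Protocol 8.5.1.3 describes one question that "asks subjects to evaluate the overall bothersomeness of their CAH symptoms". SAP 9.6.5 says "Subjects scored their most bothersome symptom (symptom was not collected"), with the score and its change summarised as a continuous variable.

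**Declared changes.** SAP 5.1.1 lists acne and hirsutism, semen analysis, and menstrual cyclicity.

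**The concern.** A section headed as changes to the protocol's analyses invites the reader to treat it as complete. It already covers exploratory endpoints, including one dropped because no samples were collected, so the sponsor evidently regards such changes as worth declaring. Four others are left out.

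The practical harm differs by item. A table titled for insulin that contains no insulin can lead a reader of the study report to believe the endpoint was reported. An objective on adrenal hormones with no planned summary leaves its status unclear: never measured, measured and omitted, or overlooked. A total score with no scoring rule cannot be reproduced and can be settled after the data are seen. It also mixes unlike content. The interview asks about acne and hirsutism, which the protocol's background attributes to androgen excess, alongside nausea, which protocol 7.2.4 gives as a sign of acute adrenal insufficiency. Because 5.1.1 removes the clinician-rated acne and hirsutism summaries, the interview items are what remains on those signs among the planned efficacy summaries, and a total does not show them. Finally, if the bother question really refers to an unrecorded worst symptom, a subject's baseline and Week 12 ratings may concern different symptoms, and their difference is hard to interpret.

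**Working it through.** The documents state no figure on this point to reproduce. The check traces each item through both documents and then looks at what the undefined total could do.

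| Item | Protocol endpoint and analysis (3, 9.3.6) | SAP endpoint (3.2.3) | SAP analysis | Named in SAP 11.3 | Declared in 5.1.1 |
|---|---|---|---|---|---|
| Fasting insulin | Endpoint; descriptive change | Absent | Absent from 9.6.3 | Only in the title of 14.2.9 | No |
| Exploratory adrenal hormones | Endpoint; descriptive change and test | Absent | Absent from 9.5.1 | No table or figure | No |
| CAH interview | Endpoint; counts, percentages, shifts | Total score | Descriptive statistics of the total | Table 14.2.6; no shift table, no listing | No |
| Bother score | Endpoint; counts, percentages, shifts | Change in score | Continuous format | Table 14.2.11; no shift table, no listing | No |

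Departures declared: 0 of 4. Changes that 5.1.1 does declare: 3, all on other endpoints. The PGIC, by contrast, keeps its counts and percentages in SAP 9.6.1, so part of the same protocol sentence was carried over.

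**Data at stake.** Insulin and the adrenal hormones are each scheduled at 4 visits. With the final sample of 11 in SAP 4.3, that is at most 11 × 4 = 44 values per analyte.

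**The total score.** Protocol 8.5.1.4 lists 18 aspects on a 5-point frequency scale and mentions no total. SAP 6.6.1 to 6.6.3, where derived variables are defined, give no item set, coding, direction or missing-item rule. So:

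- *Range.* If items are coded 0 to 4, the total runs from 0 to 18 × 4 = 72. If coded 1 to 5, it runs from 18 to 18 × 5 = 90. Both codings are assumptions.
- *Direction.* Aspects such as general health status, activity level, sleep and appetite are not plainly symptom frequencies. If m items are scored against the others, a 1-point worsening on every aspect moves the total by 18 − 2m. That is 18 when m = 0 and 18 − 8 = 10 when m = 4 (an illustrative choice).
- *Masking.* Nine items worse by 1 and nine better by 1 give 9 × (+1) + 9 × (−1) = 0. The protocol's shifts, shown by item, would reveal all 18 movements.

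These examples show what an undefined sum permits. They do not predict the data.

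**Bother score.** The two documents describe different quantities: overall bother from the disease, and the rating of one symptom whose identity was not recorded. The instrument itself is in neither document, so which description is accurate cannot be settled from them.

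**The case against.** Several counter-arguments carry weight.

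- **The insulin table is not empty of endpoints.** HbA1c and fasting glucose are protocol endpoints. A reader might infer that Table 14.2.9 reports something the protocol never asked for; it does not. It reports two valid endpoints under a misleading title and omits a third.
- **The data may still be listed.** SAP section 6 promises listings of all data, the listings titled Baseline Hormones and Post Baseline Hormones name no analytes, and the index may be updated after finalisation. A reader might infer that the adrenal hormones or interview items will appear nowhere; the documents do not establish that. What is established is that no named summary covers the hormones and no named listing covers the interview.
- **The assays may not have been run.** Protocol 8.5.3 says the adrenal-hormone samples are stored and describes the panel as one that may include certain steroids. The SAP schedule lacks insulin and also differs from the protocol on screening length and on the period of glucocorticoid stability before baseline, so it may follow another protocol version (an inference). If so, the remedy is a declaration, as was made for semen.
- **A total would not hide harm.** A reader might infer that worsening nausea or dizziness would be cancelled out and lost. Adverse events are reviewed at every visit from baseline and tabulated separately, so the safety analysis does not depend on the interview.
- **The objective is broader than insulin.** It names metabolic parameters, and glucose, HbA1c, lipids, weight and BMI are all summarised. A reader might infer that it becomes unanswerable; on the metabolic side it loses one component.
- **Some of the contrast is one of degree.** The interview total is a different summary of the same instrument. The protocol does not state that its counts and shifts are by item, although no other level is described. The SAP's continuous format for the bother score includes median, quartiles and range, so it is not a mean alone.

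These limit the consequence. They do not supply the missing insulin summary, the missing adrenal-hormone analysis, a definition of the total, or an entry in 5.1.1. An updated index would not repair 3.2.3, 9.6.1, 9.6.3 or 9.6.5.

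**Conclusion.** The point holds as one of undeclared departures and incomplete exploratory reporting. Two protocol endpoint sets have no named summary, one instrument is reduced to an undefined score, and one question is described in two incompatible ways. None of the four is among the three declared changes. Followed as written, the SAP leaves protocol commitments unmet and gives one table a title its contents do not support.

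The size is modest. Every item is exploratory, in an open-label, single-arm study that the SAP calls hypothesis-generating, with a final sample of 11. The primary safety conclusion and the secondary hormone conclusions are unaffected.

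Two assumptions apply. Section 5.1.2 (revisions to SAP version 1.0) could not be seen, so the absence of a declaration is verified for 5.1.1 only. The documents also do not show whether insulin and the adrenal hormones were assayed, so the choice between adding a summary and adding a declaration rests with the sponsor's knowledge of the data.

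**What to change.** 1. Add fasting insulin to SAP 3.2.3, 9.6.3 and Table 14.2.9. If it was not assayed, say so in 5.1.1 and retitle the table for glucose and HbA1c.
2. Add a by-visit summary in the GM format of whichever exploratory adrenal hormones were measured, with the protocol's test of change or a statement that it is dropped. If none was measured, say so in 5.1.1.
3. For the CAH interview, restore counts, percentages and shifts from baseline, by item, with a by-subject item listing. Keep a total only as a secondary summary with its items, coding, direction and missing-item rule stated.
4. Check the bother question as administered, correct whichever of protocol 8.5.1.3 or SAP 9.6.5 misdescribes it, and add the protocol's counts and shifts beside the continuous summary.
5. List every remaining departure, with its reason, in 5.1.1.

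The cost is a few tables and listings for 11 subjects where data exist, and a few sentences where they do not. There is no added patient burden. Laboratory cost arises only if the sponsor chooses to assay stored samples.
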